11.2. Description of Statistical Methods

The statistical analysis is the responsibility of the NDORMS OSIRIS Trial Statistician. A full statistical analysis plan will be written and agreed by the Trial Steering Committee before any analyses are undertaken, and all reporting will follow the CONSORT reporting guidelines.

All primary analyses will follow an 'intention to treat' (ITT) principle, with all participants included in the analyses based on the treatment arm to which they were initially randomised, regardless of their compliance with the protocol.

The analysis of this study will be performed after all participants have completed their 12-month post intervention assessment. Data will also be analysed with respect to health economics.

The primary outcome of dislocation rate will be calculated in each group. Data will be examined for distribution and the most appropriate statistical test used. If the data are normally distributed, a two-sample t-test to compare groups may be the most appropriate. Multivariate linear regression analysis will be used to identify differences between the treatment groups using separate two-way comparisons (best practice THA surgical technique and templating versus best practice THA surgical technique with OPS-guided templating). The model will be adjusted for relevant baseline characteristics.

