11. STATISTICS

11.1. The Number of Participants

The study's aim is to determine whether the Corin OPS system reduces dislocation rate, compared to standard surgical technique and templating. A literature review found that the dislocation rate after THA was 5.0%^{11,17,18}. A clinically significant difference of interest of 4.5% will be used in this study, meaning the required dislocation rate in the OPS group is <0.5%. We performed a power calculation, with α significance of 0.05 and power of 0.8, which gave a required sample size of 414 participants. Accounting for a dropout rate of 10%, this gives a total required sample size of 460, with 230 participants in each arm.

The first 100 participants recruited will be entered into an internal pilot study. The internal pilot study will study the rate of recruitment of participants and analyse whether completion of recruitment of all patients is feasible within our time limits. If the internal pilot study shows that completing the study is unfeasible, then the full trial will be terminated. The internal pilot study will allow calculation of a provisional dislocation rate (the primary outcome) in the control arm of the study. The rationale for this is that the control arm participants may have a different dislocation rate to that found in our literature review. Using the dislocation rate in the internal pilot study and the minimum clinically significant difference of interest, we will re-calculate the sample size required to fully power the full study. We expect, therefore, that the full study sample size may change by 5% either way from our projected sample size of 476 participants. However, if the size of the cohort increases by more than 5% (to above 500) we may need to re-approach the funder to enable us to recruit additional participants.

The subgroup of 50 participants receiving gait analysis pre-operatively and at 12-month post-operatively will include 25 participants from each study arm. The sample size of 50 is of sufficient size to give detailed information. Analysis on a larger group is not possible due to gait laboratory capacity constraints.

The subgroup of participants receiving a 12-month post-operative CT scan will include 50 participants from the OPS arm. The position of the implant compared to the planned position will be analysed. The sample size of 50 is of sufficient size to give detailed information. Analysis on a larger subgroup is not possible due to financial constraints.

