11.3. The Level of Statistical Significance

All hypothesis testing will be performed at the two-sided 5% level of significance.

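### Section 11.2 names methods for continuous data after the primary outcome, dislocation, and fixes no two-proportion test, effect measure or interval; the harm is modest and the remedy is wording.

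*Combined protocol and SAP*

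**What the plan says.** The analysis of the primary outcome is set out in four sentences of section 11.2. The outcome comes first: "The primary outcome of dislocation rate will be calculated in each group". Next comes the rule for choosing a test: "Data will be examined for distribution and the most appropriate statistical test used". The only test named is conditional: "If the data are normally distributed, a two-sample t-test to compare groups may be the most appropriate". Then comes the model: "Multivariate linear regression analysis will be used to identify differences between the treatment groups using separate two-way comparisons". On covariates it says: "The model will be adjusted for relevant baseline characteristics".

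Section 11.1 treats the same outcome as a proportion. It takes 5.0% in the control arm and a difference of 4.5 points, "meaning the required dislocation rate in the OPS group is <0.5" per cent. It also has the internal pilot provide "calculation of a provisional dislocation rate (the primary outcome) in the control arm of the study". Section 11.3 sets the error level: "All hypothesis testing will be performed at the two-sided 5% level of significance".

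The synopsis and section 5 list re-operation for dislocation beside the dislocation rate, and section 4 says that dislocation often recurs. Section 11.2 deals with neither. Age band and sex are minimisation factors (sections 6 and 8.4) but are not tied to the model. Sections 11.2 and 11.7 promise a full SAP, agreed by the Trial Steering Committee before any analysis. No chi-square, Fisher, logistic or risk-difference method and no confidence interval is named for dislocation.

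**The concern.** The sample size assumes a comparison of two proportions, while the analysis text that follows the primary outcome describes methods for continuous data. A yes/no outcome that occurs in a few per cent of participants is never normally distributed. The one stated criterion therefore fails every time and does not say what to do next.

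Three things are left open: which test decides the trial, how the treatment effect and its uncertainty are reported, and which covariates enter a model with about 11 events in total. With so few events, standard tests can fall on opposite sides of 5%, and an interval that assumes a symmetric estimate can be poorly balanced.

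**Working it through.** **Inputs.** Control 5.0%, OPS 0.5%, alpha 0.05, power 0.80, 414 evaluable, 10% dropout and 460 in total (section 11.1); two-sided testing (section 11.3); 1:1 allocation (section 8.4). An OPS rate of 1.5% is my assumption, used to test sensitivity.

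**1. Reproduce the plan's figure.** Uncorrected two-proportion formula, with p̄ = (0.05 + 0.005)/2 = 0.0275:

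n = [1.960·√(2·0.0275·0.9725) + 0.8416·√(0.05·0.95 + 0.005·0.995)]² / 0.045²
= (0.4533 + 0.1928)² / 0.002025 = 206.1, so 207 per arm and 414 in total; 414/0.9 = 460.

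Both figures match. The design thus treats dislocation as yes/no per participant. That is an inference, since the documents do not define whether the rate counts participants or events.

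**2. Expected events at 207 per arm.** Control 207 × 0.05 = 10.4; OPS 207 × 0.005 = 1.0. The chance of no OPS events is 0.995^207 = 35.4%.

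**3. Does the test matter?** I enumerated the tables as two independent binomials, two-sided 5%.

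| Control 5.0% v OPS 0.5% | 207 per arm | 230 per arm |
|---|---|---|
| Power: t-test, uncorrected chi-square, score test | 86.3% | 90.1% |
| Power: Fisher, continuity-corrected chi-square | 77.6% | 83.2% |
| Score and Fisher verdicts differ | 8.6% | 6.9% |

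At 207 per arm the t-test, uncorrected chi-square and score test agree in all 208 × 208 = 43,264 tables. Their type I error is 4.8% at a common rate of 5% or 2.75%. Two borderline tables at 207 per arm:
- 9 v 2: p = 0.032 (chi-square, t-test) against 0.062 (Fisher).
- 5 v 0: p = 0.025 (score) against 0.061 (Fisher).

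At the expected table, 10 v 1, every test is significant (p from 0.006 to 0.015).

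**4. Is the linear-model interval sound?** Without covariates it is d ± t·√{[q₁(1−q₁) + q₂(1−q₂)]/(n−1)}, where q₁ and q₂ are the observed proportions in the control and OPS arms and d = q₁ − q₂. The table gives the share of trials in which the 95% interval lies wholly below, then wholly above, the true difference. Balanced misses would be 2.5% on each side.

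| Setting | Linear model | Miettinen-Nurminen |
|---|---|---|
| 207 per arm, OPS 0.5% | 4.5%, 0.9% | 2.0%, 2.7% |
| 230 per arm, OPS 0.5% | 5.2%, 1.2% | 1.8%, 3.2% |
| 207 per arm, OPS 1.5% | 3.6%, 1.3% | 2.1%, 3.3% |
| 230 per arm, OPS 1.5% | 3.7%, 1.4% | 2.2%, 3.3% |

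Example, 10 v 0 at 207 per arm: d = 10/207 = 4.83 points, standard error √(0.0483 × 0.9517/206) = 1.49 points and t = 1.966, giving 1.9 to 7.8 points. Miettinen-Nurminen gives 2.6 to 8.7.

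**The case against.** The strongest defence is that the text does not force a wrong test. It calls for whatever test is most appropriate, makes the t-test conditional and tentative, and promises a SAP before any analysis. For 0/1 data the condition fails and a binary test remains open. The regression sentence may also be meant for continuous outcomes such as the Oxford and Harris hip scores. All of this stands as mitigation, but it postpones the choice without making it. If the regression sentence does not cover dislocation, the primary outcome has no specified analysis at all.

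A second defence is that the named methods do little damage. The t-test reaches the chi-square verdict, and linear regression on 0/1 data estimates a risk difference, the scale on which the 4.5-point target is set. This also stands. The extra misses of the linear-model interval understate the benefit, and total coverage stays near nominal: 100 − 4.5 − 0.9 = 94.6% at 207 per arm, and about 93.5% at 230 by the unrounded figures. The imbalance is almost fivefold at 207 per arm and the design rates, but about 2.6 to 2.7 times if the OPS rate is 1.5%. Miettinen-Nurminen is not perfectly balanced either; its misses lean the other way, and less.

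Third, Fisher's test is named nowhere in the documents. Its lower power shows what an open choice could cost and does not describe the plan as written.

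**Conclusion.** The point holds as a mismatch and an omission in the primary analysis, with modest consequences. Section 11.2 pairs a rare binary outcome with a criterion that cannot select a test for it. It leaves the effect measure, interval and covariates unstated, while section 11.1 rests on a two-proportion comparison.

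Two stronger readings are tempting, and the documents do not support them:
- **The plan would give false-positive results or invalidate the trial.** The unadjusted t-test holds type I error at about 4.8% and loses no power against the uncorrected chi-square.
- **The plan is underpowered because of its test.** Power falls below 80% only if Fisher or a continuity correction is chosen and the full 10% is lost; with 230 per arm evaluable, Fisher has 83.2%.

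What remains is an unbalanced interval under the linear model (4.5% v 0.9% at 207 per arm, 5.2% v 1.2% at 230, about 3.6% v 1.4% if the OPS rate is 1.5%). There is also an open test choice that could change the verdict in 7% to 9% of trials at the design rates. These figures assume one yes/no result per participant, independent participants, no covariate adjustment and a control rate of 5.0%.

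**What to change.** In section 11.2 and the promised SAP:

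1. Remove the distribution check, t-test and linear regression for dislocation. Keep them for the continuous outcomes, with covariates listed.
2. Define the primary outcome as the proportion of participants with at least one dislocation by 12 months, for the sponsor to confirm. Report re-operation for dislocation separately.
3. State how participants lost before 12 months enter the denominator, since section 11.6 includes everyone randomised.
4. Name one deciding analysis that matches the sample-size formula: the uncorrected two-proportion score test, two-sided 5%, with the matching Miettinen-Nurminen 95% interval for the risk difference.
5. Limit any adjusted model to arm, age band and sex, using a binary-outcome method that tolerates a zero cell, given the 35.4% chance of no OPS events at the design rates. The particular method, and any exact sensitivity test, can be left to the trial statistician.

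The cost is wording and slight extra analysis work, with no additional patients or data and no power lost against the unadjusted t-test. The downside is that the score test is approximate: for common rates up to 10% its maximum type I error is 5.0% at 207 per arm and 5.05% at 230.

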11.3. The Level of Statistical Significance

All hypothesis testing will be performed at the two-sided 5% level of significance.

11.4. Criteria for the Termination of the Trial

The trial will be terminated at the one year follow up for all participants, or if any serious adverse outcome related to use of the pelvic screw or the laser assembly system were to become apparent during the trial, the leading members of the trial would meet to determine the nature of the outcome and decide upon the need to terminate the trial.

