The factors that influence dislocation are poorly understood. Conventional surgical wisdom dictates that placing a cup in the Lewinneck 'safe zone' reduces both instability and wear¹³. A recent study of 9784 primary THAs, however, demonstrated that 58% of patients who suffered a dislocation had implants judged to be in a safe position¹⁴. This has led to suggestions that the idea of one generic 'safe zone' may be misleading^{14,15}; instead, there is a unique optimum position to place a cup in each patient undergoing THA, based on the unique and complex interaction of the spine and pelvis of the individual. Thus, in some patients, whilst the acetabular cup appears well positioned by conventional measures, pelvic tilt and spinal position mean that the cup is placed in a position of instability during some activities.

The Corin Optimised Positioning System (OPS) is a novel platform, designed to enable delivery of the prosthetic acetabular cup into an optimised position for every patient undergoing THA¹⁶. It comprises two stages: pre-operative planning and intra-operative guidance. Pre-operatively, patients undergo dynamic imaging (computed tomography scanning and X-ray films). The information gained about the relative movements of a patient's spine, pelvis and hips are used to create a personalized physiological profile. This enables calculation of the optimized acetabular cup orientation for each individual. A unique physical guide (which falls under the definition of a custom-made device in the Medical Device Directive) is then created for each patient to fit precisely into the acetabular fossa, for use intra-operatively. Intra-operatively, the Corin OPS uses laser alignment to aid the surgeon in aligning the acetabular cup in the calculated optimised orientation. One laser is affixed to an immovable pelvic screw; the other is attached to the reverse of the acetabular cup. The target orientation of the cup is achieved when the two lasers are aligned.

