8.4. Randomisation, blinding and code-breaking

Following written informed consent and confirmation of eligibility, all patients will be randomised into the study. Patients will be allocated a study number and will be randomised on a 1:1 basis to receive one of the two treatment options. During study recruitment, 50 participants (25 in each study arm) will be randomly selected to undergo gait analysis. At the end of study recruitment, 50 participants will be randomly selected from arm 2 (OPS arm) of the study cohort to have a second CT scan, which will be performed at 12-months post-operatively.

Randomisation will be performed using an automated computer-generated minimisation system through the Oxford Surgical Interventional Trials Unit to age (<40, ≥40 and <65, or ≥65), and gender. This process will occur centrally in Oxford and be overseen by the trial coordinator. Investigators at other sites will contact the site in Oxford to get each participant's randomisation allocation. Patients will be blinded as to which arm of the trial they have been allocated. The Oxford trial coordinator, the operating surgeon and the theatre staff will be unblinded and aware of which treatment arm the patient is in. The post-operative care team will remain blinded.

The Oxford trial coordinator will retain a full list of all recruited patients, their anonymous code number, and the treatment arm they have been allocated to. Trial coordinators at other sites and all operating surgeons will have access to a partial list, containing the same information on patients recruited at their own site only.

They will be the only people with access to this list. They will not have any role in collecting, reviewing, or interpreting post-operative data. Members of the research team who will be post-operatively assessing patients clinically, reviewing images or collecting and interpreting PROMs data will be blinded to patient allocation.

We do not anticipate a situation where code breaking will be required because the surgeons are not blinded to which arm the patients are in.

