9. DESCRIPTION OF PROCEDURES

THA will be performed under general anaesthesia or spinal anaesthesia. The surgical technique will be standardised across all sites. All surgeons operating within the trial perform in excess of 60 hip arthroplasties annually. THA will be performed via anterior, antero-lateral, lateral or posterior approach. The study will use the Corin Trinity shell system for the acetabular system. The study will use all compatible Corin stem implants (MiniHip, TriFit, MetaFix and TaperFit) for the stem implant. All head and stem sizes will be included in the trial. All implants will be supplied by Corin Ltd. Pre-operatively all patients (both arms) will undergo dynamic imaging (computer tomography scanning and X-ray films) of their pelvis and hips.

Arm 1: Best practice total hip arthroplasty (THA) with conventional templating

An antero-posterior view radiograph of the pelvis (with legs positioned in 15° internal rotation) and a lateral view radiograph of the hip are required for conventional templating. The radiographs will be examined pre-operatively and appropriately sized cup and stem implants selected for each patient. Intra-operatively, the surgeon may select a different sized implant to that predicted by templating if clinically appropriate.

Arm 2: Best practice total hip arthroplasty (THA) with Corin OPS to guide templating

Patients in the intervention arm will undergo an identical total hip arthroplasty operation. The difference will be the templating procedure used to accurately align the acetabular cup.

The pre-operative dynamic imaging of patients in the OPS arm will be used to calculate the personalised target orientation of the acetabular cup in each patient. A unique physical guide is then created for each patient, which facilitates the accurate positioning of the prosthetic acetabular cup. The guide is a model that fits precisely into the acetabular fossa.

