At the appropriate step during the operation, the acetabular fossa is cleared of the fat pad and remnants of the ligamentum teres. Cartilage is removed from areas within the acetabulum where the arms of the guide will sit. The guide is then placed accurately into the acetabular fossa, using guide-holding forceps. Five reference markings on the model assist with accurately locating the guide. Superomedial pressure is applied to ensure it is fully seated within the fossa and rigidly stable. An acetabular laser assembly is then attached to the back of the guide. A pelvic screw is screwed into the bone either around the acetabulum within the incision or percutaneously into the iliac crest. Once the screw is fixed rigidly, a pelvic laser assembly is attached to the back of the pelvic screw. The alignment of the pelvic screw laser is then

adjusted until the laser converges with the laser of the acetabular guide, as projected onto the operating theatre wall or ceiling. The pelvic laser is secured with a dial.

The acetabular laser assembly is then detached from the guide, and the guide is removed from the acetabulum. The pelvic laser assembly is detached from the pelvic screw. The acetabulum is reamed as per the routine technique. The pelvic laser assembly is then reattached to the back of the pelvic screw. Care is taken not to change the direction of the pelvic laser. Next, the acetabular laser assembly is connected to a magnetic impactor adaptor and attached to the back of the prosthetic acetabular cup introducer. The cup is placed in the acetabulum and the orientation is adjusted until the acetabular laser converges with the pelvic laser. The pelvic laser assembly is removed and the acetabular cup is impacted. Note that the pelvic laser assembly can be repeatedly attached and removed to assess alignment during impaction. Once the cup is fully impacted in a satisfactory position, the pelvic screw can be removed, and the operation completed as per the routine technique.

In both arms all intra-operative findings will be recorded on the operation note. Participants will be assessed post operatively by the physiotherapy and medical teams to ensure safety for discharge and when safe patients will be discharged home in line with standard routine care. After discharge, all patients will follow an identical physiotherapy regime, which will follow standard practice after total hip arthroplasty.

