10. SAFETY REPORTING

Surgery

All participants will be recruited from a population that are on waiting lists for total hip arthroplasty surgery at one of the participating centres. All procedures will be carried out in accordance with existing practice and therefore participation in the study will not confer any increased risk. Surgical risks are minor and rare but include infection, thromboembolism, persistent pain, bleeding, damage to nerves of blood vessels, stiffness, injuries caused by traction and failure of procedure.

The insertion of the pelvic screw into the pelvis is the additional step in the intervention arm that carries risk. Risks from this part of the procedure would be similar to those of the control arm surgery itself in terms of pain, bleeding, infection, damage to nerves or blood vessels, or failure of procedure. The risk of infection in both procedures is minimised by the use of prophylactic antibiotics. Complications from the surgery will be monitored as per each NHS trust protocol for routine postoperative care. This involves regular monitoring by nursing staff and doctors for evidence of postoperative complications whilst the participant is an inpatient, and at every follow up visit when the patient is an outpatient. Wound sites will be checked for evidence of infection, collections, or failure to heal, observations will be monitored for signs of infection or complication, and blood tests will be monitored for evidence of bleeding, infection, or electrolyte imbalance. The patient will only be discharged from in-patient care once both medical and physiotherapy teams agree that the patient is safe for discharge as per standard postoperative protocol.

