10.2. Reporting Procedures for Serious Adverse Events

A serious adverse event (SAE) occurring to a participant should be reported to the REC that gave a favourable opinion of the study where in the opinion of the Chief Investigator the event was 'related' (resulted from administration of any of the research procedures) and 'unexpected' in relation to those procedures. Reports of related and unexpected SAEs should be submitted within 15 working days of the Chief Investigator becoming aware of the event, using the HRA [report of serious adverse event](#) form (see HRA website). Any adverse event considered to be related to any devices supplied by Corin shall be submitted to Corin via <https://vigilance.coringroup.com/vigilance-form/>.

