14.4. Reporting

The CI shall submit once a year throughout the clinical trial, or on request, an Annual Progress Report to the REC, HRA (where required), host organisation and Sponsor. In addition, an End of Trial notification and final report will be submitted to the REC, host organisation and Sponsor.

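### The 11.4 safety trigger names only the pelvic screw and laser assembly, and an arm-level excess of dislocations under OPS has no stated route to review before the final analysis

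*Combined protocol and SAP*

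**What the plan says.** - **Trigger.** Apart from the planned end of follow-up, section 11.4 has one ground for considering termination: "if any serious adverse outcome related to use of the pelvic screw or the laser assembly system were to become apparent during the trial". The trial's leading members would then meet and decide.
- **What OPS changes.** The system calculates a target cup orientation for each patient. "A unique physical guide is then created for each patient, which facilitates the accurate positioning of the prosthetic acetabular cup" (section 9). During surgery, "An acetabular laser assembly is then attached to the back of the guide", and section 4 adds: "The target orientation of the cup is achieved when the two lasers are aligned".
- **Single events.** Section 10: "Complications from the surgery will be monitored as per each NHS trust protocol for routine postoperative care". Section 10.2 sends serious adverse events (SAEs) to the ethics committee when the chief investigator judges them both related and unexpected. It adds: "Any adverse event considered to be related to any devices supplied by Corin shall be submitted to Corin".
- **Aggregate information.** Dislocations are recorded in both arms at 3, 6 and 12 months (8.6). The pilot estimates the control-arm dislocation rate only, to recalculate sample size, and its stopping question is feasibility (11.1). The analysis follows the last 12-month assessment (11.2). Section 14.4: "The CI shall submit once a year throughout the clinical trial, or on request, an Annual Progress Report to the REC". It does not ask for counts by arm.
- **Who can link outcome to arm.** Of those holding the allocation list, section 8.4 says: "They will not have any role in collecting, reviewing, or interpreting post-operative data". Outcome assessors are blinded.
- **Committees.** A DMC appears only in the abbreviations (section 3). The Trial Steering Committee's only stated task is to agree the SAP (11.2, 11.7).

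**The concern.** Cup orientation is what OPS alters, and dislocation is the outcome it is meant to change. If a planned orientation is wrong, the likely harm is dislocation with the screw and lasers working as designed, and 11.4 does not clearly cover that. Section 4 says there is as yet no evidence that the approach affects dislocation, and 11.3 specifies two-sided testing, so a worse result under OPS cannot be ruled out beforehand.

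Each existing safety route turns on a judgement about one patient. Dislocation is a known complication of hip replacement, so individual cases may look ordinary, or fail the test of being unexpected, while the arm as a whole does worse. Nobody is assigned to put the two arms' counts side by side while operations continue.

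**Working it through.** **Design figure.** Section 11.1 gives 5.0% v 0.5%, α 0.05 and power 0.8. With the pooled normal formula, two-sided, p̄ = 0.0275:

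n = [1.960√(2 × 0.0275 × 0.9725) + 0.842√(0.05 × 0.95 + 0.005 × 0.995)]² / 0.045² = 206.1, so 207 per arm and 414 in total; 414/0.9 = 460.

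This matches the plan. Section 11.1 also mentions 476; I use 460, or 230 per arm.

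**Timetables.** Months run from first recruitment, with a 3-month (13-week) wait for surgery (8.6).
- A: even recruitment over two years (section 6). Last operation 24 + 3 = month 27; analysis 27 + 12 = month 39.
- B: three-year trial period (synopsis). Last operation 36 − 12 = month 24; recruitment 24 − 3 = 21 months; analysis month 36.
- C: four per week to 100 (week 25), then six per week (section 6; the switch point is my assumption). Recruitment ends in week 25 + 360/6 = 85, the last operation is in week 98, and analysis is in week 150 (about month 35).

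**OPS patients not yet operated on** = 230 − (operated on)/2. Operated on by month m is 460(m − 3)/24 for A and 460(m − 3)/21 for B. For C it is 100 + 6 × 14 = 184 at week 52 and 100 + 6 × 40 = 340 at week 78.

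| Month | A: operated on (OPS left) | B | C |
|---|---|---|---|
| 12 | 172.5 (143.8) | 197.1 (131.4) | 184 (138) |
| 18 | 287.5 (86.2) | 328.6 (65.7) | 340 (60) |
| 24 | 402.5 (28.8) | 460 (0) | 460 (0) |

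**What a listing might show.** The documents give no harm rate, so I assume 10% OPS v 5% control. The low end spreads risk evenly over 12 months and counts full-year equivalents per arm (month 12: A 32.3, B 37.0, C 31.1; month 18: 86.3, 98.6, 93.4). The high end puts all events soon after surgery and treats them as known at once (up to 99 per arm at month 12 and 170 at month 18).

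| | Month 12 (n = 31 to 99) | Month 18 (n = 86 to 170) |
|---|---|---|
| Expected dislocations, low end | 3.1 v 1.6 | 8.6 v 4.3 |
| Expected dislocations, high end | 9.9 v 4.9 | 17.0 v 8.5 |
| Chance of one-sided Fisher p<0.05 | 0.052 to 0.275 | 0.247 to 0.466 |
| Chance OPS count is no higher than control | 0.306 to 0.112 | 0.132 to 0.047 |

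**Recording lag.** If events are known only from the 3-month visit, at most about 66 per arm contribute at month 12 (460 × 6/21 ÷ 2) and 131 at month 18 (460 × 12/21 ÷ 2). The upper Fisher chances fall to about 0.19 and 0.36. Appendix B also collects adverse events as reported, so the truth may lie between.

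**False alarms.** With 5% in both arms, the OPS count exceeds control with probability 0.38 at n = 31, 0.43 at n = 86 to 99 and 0.45 at n = 170. Over two looks (timetable A, early risk, n = 86 then 144), it does so at least once in about 54% of trials.

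**Pilot.** The 100th participant enters in week 25. Operations start in week 13, so 4 × 12 = 48 have been operated on, 24 per arm, and none has reached a 3-month visit.

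**The case against.** **The existing wording may already reach dislocation.** The cup is placed by laser convergence and the guide sets the laser, so a dislocation traced to a badly seated guide can fairly be called laser-related under 11.4. Section 10.2 covers any device the manufacturer supplies. This stands for single cases. A reader might infer that dislocations are shut out of the safety provisions altogether, and the documents do not support that. What remains is an error in the planned orientation, which is not named, and an arm-level excess, which no single-case judgement would show.

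**A remit may exist elsewhere.** A DMC is listed, and a full SAP was still to be written. A reader might infer that the trial has no DMC; the text shows only that this protocol gives it no task. The point is limited to the public text, and a cross-reference to a charter could settle most of it.

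**Early counts are weak evidence.** This also stands. Even with risk doubled, the OPS count would be no higher than control in 11-31% of trials at month 12. It argues against a formal rule or an automatic trigger, not against informed people seeing the counts.

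**By-arm counts of the primary outcome could leak.** This is a real cost, and it limits who may produce and see them.

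**Conclusion.** The gap holds in the public text. Following the plan as written, an OPS-arm excess of dislocations need not be seen by anyone until about months 35-39. A review at month 12 would come with about 131-144 OPS patients still awaiting surgery, and at month 18 with about 60-86. By month 24 the figure is 0-29, so a yearly cycle alone would be late on two of the three timetables.

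These counts rest on 460 participants, equal arms, no dropout before surgery and the stated recruitment pace. The detection figures rest on an assumed doubling of risk and are illustrations only. A reader might infer that an early look would reliably catch harm, or that harm is likely. Neither follows: the documents give no OPS harm rate, and the chances computed above stay below one half throughout. The point is a worthwhile, inexpensive safety improvement and does not affect the validity of the final comparison.

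**What to change.** 1. Reword 11.4 so that review follows a serious adverse outcome related to any OPS component: planned cup orientation, patient-specific guide, pelvic screw or laser assembly.
2. State that closed by-arm counts of dislocations, re-operations for dislocation and SAEs, without hypothesis tests, go at about months 12 and 18 to the DMC, or to steering committee members independent of surgeons and assessors. They may recommend review under 11.4 if they judge an imbalance to be a safety concern.
3. Do not make a numerically higher OPS rate an automatic trigger, and do not schedule a listing at the pilot review, when it would be nearly empty.
4. Have the table produced by someone who sets neither the analysis nor the sample size. If the trial statistician must do it, agree the SAP and record the pilot sample-size recalculation first.

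Cost: an amendment to one section, a short table from data already collected, a brief remit, possibly some independent members, and some time from a second statistician. No extra visits or patients are needed. The downside is that a few people see by-arm counts of the primary outcome, so these must be kept from surgeons, assessors and those setting the analysis or sample size.
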